2.2 Overall Study Duration and Follow-Up

The study period will consist of a Screening Visit within 4 weeks of Baseline, a Treatment Period of 96 weeks and a final Follow-Up Visit. Subjects will receive treatment for 96 weeks. The total duration of subject participation will be up to 104 weeks.

2.2.1 Screening

Subject eligibility for the study will be determined within 28 days prior to study entry. If required per local guidelines and if not already available within the previous 3 months, an MRI scan should be performed locally before starting therapy with BG00012.

2.2.2 Treatment Period

[figure not shown]
Eligible subjects will report to the study site every 4 weeks for the first 12 weeks and every 12 weeks thereafter for 96 weeks.

Discontinuation and/or Withdrawal Visits [REDACTED] Visits will be performed as necessary. Subjects who withdraw from the study early will be asked to return to complete a Discontinuation and/or Withdrawal Visit within 2 weeks of their last study treatment dose.

2.2.3 Follow-Up

Subjects are to return to the study site for a Follow-Up Visit 4 weeks after their last dose of study treatment. The final study visit will be Week 100.

[figure not shown]
Subjects who temporarily withhold or permanently discontinue BG00012 for any reason and have a lymphocyte count <LLN will be followed every 4 weeks for 24 weeks, then every 12 weeks (**unless clinically indicated more often or at the Investigator's discretion**) until the lymphocyte count is \geq LLN or for up to 48 weeks following drug discontinuation, whichever occurs sooner). Subjects whose lymphocyte count remains <LLN at the end of the study (Week 96) will complete the final Follow-Up Visit and will then be followed up outside of this protocol at the Investigator's discretion.

CONFIDENTIAL

The information contained herein may not be used, disclosed, or published without the written consent of Biogen Idec MA Inc.

	
Protocol 109MS310 An Open-Label Study to Assess the Effects of BG00012 on Lymphocyte Subsets in Subjects With RRMS
	Final Version 1.0
---	---	--------------------------

2.2.7 Additional Assessments if Required by Local Tecfidera Prescribing Information

Any additional assessments that are needed to comply with the local prescribing information for Tecfidera should also be performed and will be reimbursed by Biogen while a subject is participating in this study.

2.3 Study Stopping Rules

There are no study-specific stopping rules. Biogen may terminate this study at any time after informing Investigators. Biogen will notify Investigators when the study is to be placed on hold, completed, or terminated.

CONFIDENTIAL

The information contained herein may not be used, disclosed, or published without the written consent of Biogen Idec MA Inc.

biogen idec	Protocol 109MS310 An Open-Label Study to Assess the Effects of BG00012 on Lymphocyte Subsets in Subjects With RRMS	Final Version 1.0
--------------------	---	--------------------------

2.4 End of Study

The end of study is last subject, last visit for final collection of data.

3 INTERIM ANALYSIS

In general, since this is an ongoing phase 3b study, interim analyses will be performed as needed for regulatory reporting, safety updates, publications, or as otherwise required by the Sponsor.

4 SAMPLE SIZE JUSTIFICATION

The sample size for this study is not based on formal hypothesis testing but on the precision of the estimation of the primary endpoints and the ratios between various ALC subgroups.

For example, the Phase 2 and 3 controlled and uncontrolled efficacy and safety studies in MS, based on data available as of May 2014 from 2470 subjects with at least 1 post-Baseline value from the interim analysis of the Integrated Summary of Safety of Tecfidera, showed that 76% of subjects had all ALC values \geq LLN and 24% had at least 1 ALC value $<$ LLN up to Week 48. Assuming the same proportion of subjects in this study will have 1 or more ALC values $<$ LLN, it is expected that approximately 137 subjects will have all ALC values \geq LLN and approximately 43 subjects will have at least 1 ALC value $<$ LLN at Week 48, based on a total of 180 evaluable subjects at Week 48. With this sample size, the 90% CIs for the ratio of the 2 subgroups for the change from Baseline at Week 48 in lymphocyte subsets are illustrated below using the scenario of a true ratio of 0.8 (20% decrease) and 0.7 (30% decrease), respectively. When assessing lymphocyte subsets between subjects with at least 2 ALC values $<$ LLN up to the first 48 weeks of treatment versus subjects who have all ALC values \geq LLN throughout the study, the 90% CIs of the ratio would be wider, as historical data suggest that 16% of the patients treated with Tecfidera may have 2 or more ALC values $<$ LLN during the first 48 weeks of treatment.

To allow for a 10% discontinuation rate, a total of 200 subjects are planned for enrollment.

Table 3: Sample Size Calculations

Primary Endpoints	SD ^{a)}	Ratio	90% CI for the Ratio Based on N = 180	
			Subjects With At Least 1 ALC $<$ LLN ^{b)} vs. Subjects With All ALC \geq LLN ^{b)}	Subjects With At Least 2 ALC $<$ LLN ^{b)} vs. Subjects With All ALC \geq LLN ^{b)}
	0.32	0.8	0.73, 0.88	0.71, 0.90

CONFIDENTIAL

The information contained herein may not be used, disclosed, or published without the written consent of Biogen Idec MA Inc.

biogen idec	Protocol 109MS310 An Open-Label Study to Assess the Effects of BG00012 on Lymphocyte Subsets in Subjects With RRMS	Final Version 1.0
--------------------	---	--------------------------

Primary Endpoints	SD^{a)}	Ratio	90% CI for the Ratio Based on N = 180	
			Subjects With At Least 1 ALC <LLN^{b)} vs. Subjects With All ALC ≥LLN^{b)}	Subjects With At Least 2 ALC <LLN^{b)} vs. Subjects With All ALC ≥LLN^{b)}
CD4 T cell count		0.7	0.63, 0.77	0.63, 0.78
CD8 T cell count	0.35	0.8	0.72, 0.89	0.71, 0.91
		0.7	0.63, 0.78	0.62, 0.79
CD56 ^{bright} NK cell count	0.57	0.8	0.68, 0.95	0.65, 0.98
		0.7	0.59, 0.83	0.57, 0.86
T _{reg} count	0.95	0.8	0.60, 1.07	0.57, 1.12
		0.7	0.52, 0.93	0.50, 0.98

ALC = absolute lymphocyte count; CD = cluster of differentiation; CI = confidence interval; LLN = lower limit of normal; NK = natural killer; SD = standard deviation; T_{reg} = T regulatory; vs. = versus.

^{a)} Common standard deviation for the log-transformed change from Baseline.

^{b)} Up to Week 48.

5 STATISTICAL ANALYSIS METHODS

5.1 General consideration

The statistical software, SAS[®], will be used for all summaries and statistical analyses.

This study only includes a single arm. In general, statistical analyses will be descriptive in nature with appropriate measures of variation provided where applicable. For continuous endpoints, number of subjects in the analysis population, number of subjects with non-missing observations, mean, standard deviation (SD), median, minimum and maximum will be reported. For categorical endpoints, number of subjects in the analysis population, number with non-missing observations, and the percent of those with data in each category will be summarized.

Several analysis populations are defined for different analysis purposes in this study. An overview of these analysis populations will be summarized.

- Pharmacodynamic Population - it is defined as all subjects who receive at least 1 dose of study treatment and have at least 1 pharmacodynamic measurement after Baseline.

CONFIDENTIAL

The information contained herein may not be used, disclosed, or published without the written consent of Biogen Idec MA Inc.

	Protocol 109MS310 An Open-Label Study to Assess the Effects of BG00012 on Lymphocyte Subsets in Subjects With RRMS	Final Version 1.0
---	---	--------------------------

- Safety Population – it is defined as all subjects who receive at least 1 dose of study treatment.

- [REDACTED]

[REDACTED]

In general, for data that are summarized by visit, any early withdrawal, unscheduled or scheduled visits will be assigned to an appropriate scheduled visit by using a mid-point of the two visits windowing scheme. The date of first dose will be the reference point. The detailed windowing rules for lymphocyte subsets, hematology, blood chemistry and vital signs are available in [Appendix 2](#). After windowing, if there is only 1 record in the visit window, then this record will be selected; if there are multiple records falling into the same visit window with different distance from the target day then select the one closest to the target day; if there are 2 visits with the same distance from the target day, but one is before the target day and the other is after the target day, then select the later one; for laboratory test, if more than one observation falls in the same distance from the target regular scheduled visit day, the mean observation will be calculated and used in the summary statistics and analyses.

No imputation will be used for missing data in this study. The observed data will be used for all analyses.

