5.2. Current Therapies for Multiple Sclerosis

The most commonly used first-line MS therapies are interferons (IFNs) and glatiramer acetate (GA) [Waldman 2011]. Relative to placebo, IFNs have been shown to reduce relapse rate by approximately 27% to 36% [Calabresi 2014; Jacobs 1996; PRISMS Study Group 1998; The IFNB Multiple Sclerosis Study Group 1993], and GA by approximately 30% [Johnson 1995]. The interferon beta-1a (IFN β -1a) products have also been shown to delay disability progression [Jacobs 1996; PRISMS Study Group 1998].

Other currently approved therapies for MS include the following:

- Natalizumab: a humanized monoclonal antibody directed against α 4 integrins [Polman 2006].
- Fingolimod: a selective oral immunosuppressant that is metabolized to a functional antagonist of sphingosine 1-phosphate receptors on lymphocytes [Kappos 2010].
- Mitoxantrone: a synthetic antineoplastic anthracenedione that intercalates into deoxyribonucleic acid (DNA) and interferes with ribonucleic acid (RNA) [Chitnis 2012].
- Teriflunomide: an immunomodulatory drug inhibiting pyrimidine synthesis by blocking dihydroorotate dehydrogenase [O'Connor 2011].
- Alemtuzumab: a humanized monoclonal antibody targeting cluster of differentiation (CD) 52 antigen expressed on the surface of most leukocytes [Coles 2012].

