7. STUDY DESIGN

7.1. Study Overview

This is an open-label, multicenter study to evaluate the effects of BG00012 on lymphocyte subtypes and Ig isotypes. Approximately 200 subjects will be treated in approximately 100 sites in North America and Europe.

After the Screening Visit (up to 28 days) if required per local guidelines and if not already available within the previous 3 months, a magnetic resonance imaging scan should be performed locally before starting therapy with BG00012. Subjects will then receive BG00012 treatment for 96 weeks (Treatment Period). Blood samples for lymphocyte subset analysis, as well as blood samples for the determination of each subject's complete blood count with differential, will be collected at Screening, Baseline (Day 1), and Weeks 4, 8, 12, 24, 36, 48, 60 (complete blood count [CBC only]), 72, 84 (CBC only), and 96. Clinical samples for the analysis of blood chemistries will be collected at Screening, Baseline (Day 1), and Weeks 4, 8, 24, 48, and 96. A post-treatment follow-up visit, at which safety assessments will be performed, will occur 4 weeks after the final dose of BG00012.

Subjects who temporarily withhold or permanently discontinue study treatment for any other reason than lymphopenia and have a lymphocyte count <LLN will continue protocol-required visits and assessments and will also be followed every 4 weeks for 24 weeks, then every 12 weeks (**unless clinically indicated more often or at the Investigator's discretion**) until the lymphocyte count is \geq LLN or for up to 48 weeks following drug discontinuation, whichever occurs sooner.

Subjects who develop a confirmed lymphocyte count of <500 cells/mm³ at any time during the study will be monitored every 4 weeks. If the lymphocyte count stays <500 cells/mm³ for 24 weeks, the subject will temporarily withhold study treatment. If the lymphocyte count does not recover to LLN within 24 weeks while study treatment is temporarily withheld, study treatment will be discontinued permanently (see Section 11.3).

Subjects whose lymphocyte counts remain <LLN at the end of the study (Week 96) will complete the final Follow-Up Visit and will then be followed up outside of this study at the Investigator's discretion.

Therapies directed toward the treatment of MS are permitted, at the discretion of the treating physician and only after consulting with the Medical Monitor, for subjects who have permanently discontinued BG00012 for any reason.

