 - DMF (given as Fumaderm[®]) or BG00012; enrollment will be limited to no more than 40 subjects (out of 200) with prior DMF exposure
 - cyclosporine
 - azathioprine
 - methotrexate
 - mycophenolate mofetil
 - intravenous (IV) Ig
 - plasmapheresis or cytapheresis
10. Treatment with another investigational drug or approved therapy for investigational use within 6 months prior to Baseline (Day 1).
11. Treatment with steroids (IV or oral corticosteroid treatment, including agents that may act through the corticosteroid pathway [e.g., low-dose naltrexone]) within 4 weeks (28 days) prior to Baseline (Day 1).

CONFIDENTIAL

The information contained herein may not be used, disclosed, or published without the written consent of Biogen MA Inc.

Note: Subjects who are currently using other approved disease modifying therapies (DMTs) for RRMS that are not excluded above may be included in the trial if all other criteria are met.

Subjects must discontinue these other DMT treatments upon entry into the trial. A washout period is not required by the protocol, but investigators should follow their local standards of care, taking into account the pharmacokinetic profile (ie, half-life) of the existing therapy, to manage the transition from the existing treatment to BG00012.

Miscellaneous

12. Female subjects who are currently pregnant or breastfeeding, or planning to become pregnant while in the study.
13. Current enrollment or a plan to enroll in any interventional clinical study in which an investigational treatment or approved therapy for investigational use is administered within 6 months prior to the Baseline Visit.
14. Previous enrollment in this study.
15. Inability to comply with study requirements.
16. Other unspecified reasons that, in the opinion of the Investigator or Biogen, make the subject unsuitable for enrollment.

CONFIDENTIAL

The information contained herein may not be used, disclosed, or published without the written consent of
Biogen MA Inc.

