10. DISCONTINUATION OF STUDY TREATMENT AND/OR WITHDRAWAL OF SUBJECTS FROM THE STUDY

10.1. Discontinuation of Study Treatment

A subject *must* permanently discontinue study treatment for any of the following reasons:

- The subject becomes pregnant. Study treatment must be discontinued immediately. Report the pregnancy according to the instructions in Section 15.4.1.
- The subject withdraws consent to continue study treatment.
- The subject experiences a medical emergency that necessitates permanent discontinuation of study treatment.
- The subject is unable to tolerate study treatment at 240 mg BID (see Section 11.2.4).
- The subject receives any concomitant medications not allowed by the protocol.
- The subject experiences any of the laboratory abnormalities requiring permanent discontinuation of treatment defined in [Table 3](#).
- The subject experiences more than 1 deviation of the same laboratory parameter that meets the threshold limits defined in [Table 3](#) at any time during the study.
- The subject experiences more than 2 different deviations of laboratory parameters that meet the threshold limits defined in [Table 3](#) at any time during the study. On a third occasion, the subject is required to discontinue dosing for the remainder of the study.
- If a subject has a lymphocyte count $<500/\text{mm}^3$ persisting for more than 24 weeks consecutively, study treatment must be temporarily withheld. Study treatment may be resumed after lymphocyte counts recover $>\text{LLN}$ on 2 consecutive occasions at least 4 weeks apart. If the subject develops a lymphocyte count $<500/\text{mm}^3$ on 1 occasion (confirmed by repeat testing) on resumption of study treatment, the subject must permanently discontinue study treatment and will continue protocol-required visits and assessments (see Section 11.3).
- If a subject's lymphocyte count remains $<\text{LLN}$ for 24 weeks consecutively after study treatment has been temporarily withheld due to lymphocyte count $<500/\text{mm}^3$ for more than 24 weeks, the subject must permanently discontinue study treatment.
- At the discretion of the Investigator for medical reasons or for noncompliance.

The reason for discontinuation of study treatment must be recorded in the subject's case report form (CRF).

Subjects who discontinue treatment may remain in the study and continue protocol-required tests and assessments.

CONFIDENTIAL

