11.6.1.2. Disallowed Concomitant Therapy

Concomitant treatment with any of the following is **not** allowed unless approved by the Medical Monitor:

- Any alternative drug treatments directed toward the treatment of MS, such as chronic immunosuppressant therapy or other immunomodulatory treatments (including, but not limited to, IFN- β , GA, natalizumab, cyclophosphamide, methotrexate, azathioprine, 4-aminopyridine or related products, etc.), with the exception of acute management of protocol-defined relapses (Section 11.6.3).
- Any investigational product, including investigational symptomatic therapies for MS and investigational therapies for non-MS indications.
- Any systemic steroid therapy, including, but not limited to, oral corticosteroids (e.g., prednisone) or periodic (e.g., monthly) treatment with IVMP, except for protocol-defined treatment of relapses (Section 11.6.3). Steroids that are administered by nonsystemic routes (e.g., topical or inhaled) are allowed.
- Total lymphoid irradiation, cladribine, T-cell or T-cell receptor vaccination, any therapeutic monoclonal antibody, mitoxantrone, cyclosporine, IV Ig, plasmapheresis, or cytapheresis.

The use of concomitant therapies defined above must be recorded on the subject's CRF, according to instructions for CRF completion. AEs related to administration of these therapies must be documented on the appropriate CRF.

Subjects should be instructed not to start taking any new medications, including non-prescribed drugs, unless they have received permission from the Investigator.

[figure not shown]

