Subjects whose lymphocyte counts remain <LLN at the end of the study (Week 96) will complete the final Follow-Up Visit and will then be followed up outside of this study at the Investigator's discretion.

Therapies directed toward the treatment of MS are permitted, at the discretion of the treating physician and only after consulting with the Medical Monitor, for subjects who have permanently discontinued BG00012 for any reason.

Subjects who withdraw from the study while on study treatment will complete the Discontinuation and/or Withdrawal Visit as soon as possible but no later than 2 weeks after their last dose of study treatment and will complete the final Follow Up Visit 4 weeks after their last dose of study treatment unless consent has been withdrawn.

[figure not shown]
Subjects who withdraw from the study for reasons other than safety may be replaced at the discretion of Biogen.

See [Figure 1](#) for a schematic of the study design. Refer to Table 1 and Table 2 for the timing of all study assessments.

CONFIDENTIAL

The information contained herein may not be used, disclosed, or published without the written consent of Biogen Idec MA Inc.

Figure 1: Study Design

BID = twice daily; LLN = lower limit of normal.

*Subjects will receive oral BG00012 at a dose of 120 mg BID for the first 7 days and at a maintenance dose of 240 mg BID thereafter. Temporary dose reductions to 120 mg BID may be considered.

**Subjects with a lymphocyte count <LLN will continue protocol-required visits and assessments and will have additional lymphocyte and subset analysis.

CONFIDENTIAL

The information contained herein may not be used, disclosed, or published without the written consent of Biogen Idec MA Inc.

Schedule of Activities

Table 1: Study Activities for Study 109MS310 - Table 1 of 2

Tests and Assessments	Screening	Treatment Period												Final Follow-Up Visit ⁱⁱ⁾
		Within 28 days before Baseline	Baseline (Day 1)	Week 4 (Day 28 ±3 days)	Week 8 (Day 56 ±3 days)	Week 12 (Day 84 ±3 days)	Week 24 (Day 168 ±5 days)	Week 36 (Day 252 ±5 days)	Week 48 (Day 336 ±5 days)	Week 60 (Day 420 ±5 days)	Week 72 (Day 504 ±5 days)	Week 84 (Day 588 ±5 days)	Week 96 (Day 672 ±5 days)	
Informed Consent ⁱⁱ⁾	X													
Medical History ⁱⁱⁱ⁾	X													
Hepatitis B and C Screen	X													
HIV Testing (As Per Local Guidelines) ^{iv)}	X													
Physical Examination ^{v)}	X								X				X	
Vital Signs ^{vi)}	X	X	X	X	X	X	X	X		X		X	X	
12-Lead ECG		X						X				X		

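### The SAP's off-treatment lymphocyte summaries include values taken after a switch to another MS drug; samples taken soon after relapse steroids are a smaller, related gap

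*SAP*

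**What the plan says.** **Switching.** Once BG00012 has been stopped for good, whatever the cause, Protocol 7.1 says "Therapies directed toward the treatment of MS are permitted, at the discretion of the treating physician and only after consulting with the Medical Monitor"; SAP 2.1 repeats this. Protocol 10.1 adds: "Subjects who discontinue treatment may remain in the study and continue protocol-required tests and assessments".

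**Follow-up analysis.** SAP 5.3.3 starts the lymphocyte follow-up period at dose interruption or discontinuation. It takes subjects with at least one ALC below LLN on treatment and at least one ALC in follow-up, and includes any value after the follow-up baseline. Outputs are by-visit actual value, change and percent change in ALC, with median and quartile plots, repeated for selected subsets and Ig isotypes. The last follow-up window in Appendix 2 has no upper limit.

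**Steroids.** Protocol 8.2, criterion 11, excludes IV or oral steroids "within 4 weeks (28 days) prior to Baseline (Day 1". Protocol 11.6.1.2 disallows systemic steroids on study unless the Medical Monitor approves, "except for protocol-defined treatment of relapses (Section 11.6.3".

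**Data rules.** The pharmacodynamic population is "all subjects who receive at least 1 dose of study treatment and have at least 1 pharmacodynamic measurement after Baseline". SAP 5.1 windows scheduled, unscheduled and early-withdrawal visits by day from first dose, and says "No imputation will be used for missing data in this study. The observed data will be used for all analyses". The MMRMs in 5.3.1 (to Week 48) and 5.3.2 (to Week 96) have no term or restriction for steroids, other MS drugs or treatment status. Concomitant medication is summarised (5.2.7) and, for follow-up, listed (5.4.6).

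**The concern.** The follow-up summaries are the study's description of what lymphocytes do once BG00012 is withheld or stopped. If a subject starts another MS drug during that period, later values reflect both the absence of BG00012 and the new drug. There is no control arm to separate the two. Some alternatives act directly on these cells: Protocol 5.2 describes fingolimod as a "functional antagonist of sphingosine 1-phosphate receptors on lymphocytes" and alemtuzumab as directed at an antigen on most leukocytes. A drug that lowers counts would flatten the off-BG00012 curve, and one that leaves them alone would not, so the direction depends on what subjects switch to. The ALC and Ig models in SAP 5.3.2 run to Week 96 and can take in the same values.

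The steroid gap is similar but smaller. Baseline is steroid-free by rule and later samples need not be, yet the primary endpoint is the change between them. One ALC below LLN also places a subject in the at-least-1-low group, so a sample taken soon after steroids could affect both outcome and grouping.

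**Working it through.** **1. The plan's own figures.** Enrolment: 180/(1 − 0.10) = 200, as stated. Subgroups: 180 × 0.76 = 136.8 and 180 × 0.24 = 43.2, stated as 137 and 43. CD4 row (log SD 0.32, ratio 0.8, 90% CI): 0.8 × exp(±1.645 × 0.32 × √(1/43 + 1/137)) = 0.730 to 0.877, stated as 0.73 to 0.88. The sizing is not in question.

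**2. Tracing a post-switch value.**
- Switching after permanent discontinuation is permitted (Protocol 7.1).
- Sampling can continue (Protocol 10.1).
- The value meets the inclusion wording of SAP 5.3.3 if the subject had an ALC below LLN on treatment.
- It is windowed by time alone (Appendix 2) and kept as observed data (SAP 5.1).
- No step in SAP 5.3.3 uses the start date of the new drug.

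**3. Scale of the switch effect (illustrative).** The documents give neither the share f of values at a visit that follow a switch nor the factor m by which the new drug multiplies the count. The geometric mean is multiplied by m^f:

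| f | m = 0.5 | m = 0.7 | m = 0.9 | m = 1.2 |
|---|---|---|---|---|
| 5% | 0.966 | 0.982 | 0.995 | 1.009 |
| 10% | 0.933 | 0.965 | 0.990 | 1.018 |
| 20% | 0.871 | 0.931 | 0.979 | 1.037 |

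The shift runs from under 1% to about 13%. Medians, which the SAP plots, would generally move less while f is small.

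**4. Steroid samples.** Assume 0.1 to 0.3 steroid-treated relapses per subject-year; no rate is given.
- At any one visit, subjects with a relapse in the preceding 28 days = 200 × rate × 28/365. This gives 1.5 at 0.1 and 4.6 at 0.3, or 0.8% to 2.3% of 200.
- Cumulatively to Week 48: a 28-day window always contains a scheduled sample in the first 12 weeks and does so with chance 28/84 afterwards, so the weighted chance is (12 + 36/3)/48 = 0.5. Then 200 × rate × 336/365 × 0.5 gives 9.2 at 0.1 and 27.6 at 0.3.
- The two agree, since six post-baseline visits × 1.53 = 9.2 and 6 × 4.60 = 27.6.
- At f = 2.3%, m^f is 0.992 for m = 0.7 and 0.984 for m = 0.5, a shift of about 0.8% or 1.6% at a visit.

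**5. Precision cost of exclusion.** Removing 10% of values from both groups, well above the 2.3% in step 4, moves the CD4 interval from 0.730–0.877 to 0.726–0.881.

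**The case against.** The SAP 5.1 sentence is in form a missing-data rule, not a decision about steroids or switching. That is right: the gap comes from reading it with the population, windowing and follow-up text.

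The switch route is narrow. It needs permanent discontinuation and consultation with the Medical Monitor, and the follow-up analysis also needs an earlier ALC below LLN. Subjects who cannot tolerate 240 mg BID are withdrawn from the study (Protocol 10.2 and 11.2.4). Fingolimod and alemtuzumab appear only in a background list, with nothing on who would switch to them. SAP 5.3.3 also leaves room for further exploratory analyses. All this limits the size, but none of it separates post-switch values in the planned outputs.

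Three stronger readings are tempting:
- A reader might infer that a switcher is counted as never recovering from BG00012. SAP 5.3.3 defines no recovery endpoint, rate or time to recovery; it gives by-visit summaries and plots.
- A reader might take 9 to 28 steroid-affected subjects as the contamination of the primary result. That count is cumulative over six visits, while the primary summaries and model contrasts are by visit.
- A reader might infer that a material number of subjects land in the low-ALC group because of steroids. Neither document gives the size, duration or direction of a steroid effect, so no such number can be derived. SAP 5.3.1 also has groupings on at least two low values, and on low ALC lasting 6 months or more. These are a partial check against isolated lows, although descriptive and outside the MMRM.

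Protocol 11.6.3, on relapse treatment, is not visible and may contain a sampling-timing rule. SAP 5.3.1 and 5.3.3, as visible, contain none.

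**Conclusion.** The point holds chiefly for SAP 5.3.3: as written, the off-BG00012 summaries combine withdrawal of BG00012 with whatever MS drug follows. The same values can enter the Week 96 models in 5.3.2. Before Week 48 the route is narrower, because it needs an early permanent stop. The size is unknown; the under-1% to 13% range rests entirely on assumed shares and multipliers.

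The steroid point is secondary. On assumed relapse rates it touches about 1.5 to 4.6 of 200 subjects at a visit and does not undermine the primary analysis. An all-observed-data analysis is legitimate in a descriptive study. What is missing is a companion view that lets the reader see how much the other drugs contribute.

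**What to change.** - **SAP 5.3.3:** present the by-visit summaries and plots twice, once on all observed data and once without values after the first dose of any other MS disease-modifying drug. List in advance which drugs count, and report how many subjects switched.
- **SAP 5.3.2:** apply the same exclusion as a sensitivity analysis to the Week 96 Ig and ALC MMRM.
- **SAP 5.3.1:** add one sensitivity run of the by-visit summaries and the at-least-1-ALC-below-LLN grouping without samples taken within 28 days after systemic steroids. Report how many subjects change group. The 28 days is an analysis window chosen to match criterion 11, not a clinical rule.

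These therapies are already recorded on the CRF (Protocol 11.6.1.2), and SAP 5.2.7 already has rules for partial dates. No visit, sample or treatment rule changes. The cost is SAP wording, a few extra tables and plots, and the loss of a few samples and some late follow-up values in the restricted versions. Stopping at a switch may itself be informative, since those who switch may differ from those who do not. The restricted version should therefore stand beside the all-data version and not replace it.
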